onset of stroke (Tyson, Sadeghi-Demneh, & Nester, 2013; Tyson & Kent, 2013). It is reported that the majority of the gait improvements occur within the first 6 months following the onset of stroke (Jørgensen, Nakayama, Raaschou, & Olsen, 1995; Kwakkel, Kollen, & Lindeman, 2004). However, a limited number of studies have investigated the effects of AFOs within six months of stroke onset.

Three reported studies have investigated the effects of using an AFO compared to not using an AFO within 6 months following onset of stroke. Rao et al found that the use of an AFO significantly improved gait velocity, cadence and step length on the affected and unaffected side (Rao et al., 2008). Hyun et al. found that using an AFO significantly improved VO₂ peak and 6 minute walk test scores (Hyun, Kim, Han, & Kim, 2014). Carse et al showed significant improvement in walking velocity, average step length and cadence with use of AFO. (Carse, Bowers, Meadows, & Rowe, 2014).

There is only one reported study which looked at the effects of using two different types of AFOs during the subacute stage of stroke, less than 6 months following onset. The investigators evaluated the effects of a custom Chignon AFO, which is an articulated AFO with adjustable elastic straps, compared to an off the shelf polypropylene AFO. Results of this study showed that gait speed and knee and ankle control were significantly higher in the Chignon AFO group compared to the polypropylene AFO group. Additionally, participants in the Chignon AFO group had significantly lower spasticity than those in the polypropylene AFO group (de Sèze et al., 2011).

In a recent case series report, investigators observed that using a custom Double Adjustable AFO during the early stages of recovery after stroke resulted in more typical muscle activation patterns, gait endurance and velocity, and near normal symmetry during gait without an assistive

device or an AFO in three participants (McCain et al., 2012). The authors suggested that the design of the Double Adjustable AFO may have provided more peripheral mechanical input to facilitate pre injury motor function than the typical use of AFO which is often used as a compensatory strategy for gait. The use of this type of AFO for gait rehabilitation following stroke in the subacute stages has not been thoroughly studied.

Statement of the Problem

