Reintegration to normal living is an ultimate goal of stroke rehabilitation. Difficulty in walking independently, especially outdoors, is reported as the most disabling consequence of stroke. (Pound, Gompertz, & Ebrahim, 1998). Even after rehabilitation, 63% of community dwelling stroke survivors reported dependency on others for community ambulation (Lord, McPherson, McNaughton, Rochester, & Weatherall, 2004). Gait velocity has been identified as a factor which predicts independent community ambulation in stroke survivors (Rosa, Marques, Demain, & Metcalf, 2014). Gait speed and gait endurance are also identified as predictors for community ambulation after stroke (Bijleveld-Uitman, van, & Kwakkel, 2013). Although my study is not looking at community ambulation specifically as an outcome, it is reasonable to assume that improvement in gait velocity and gait endurance with use of AFO will impact a stroke survivor's ability to improve participation in the community and to decrease caregiver dependency.

Methodology

Experimental design:

The research design for this experimental study will be a 2 factor within subject repeated measures 2x 2 design. The manipulated independent variables in the study will be 1) type of

AFO with two levels: (a) Double adjustable AFO and (b) Posterior leaf spring AFO and 2) Practice Time with 2 levels: (a) baseline, and (b) after 1 week of practice. The dependent variables in this study are the following: Gait endurance measured by 6 Minute Walk Test (6MWT), gait symmetry measured using GAITRite gait analysis system, and gait velocity measured using GAITRite gait analysis system.

Participants

Twenty participants over the age of 18, of any gender and ethnicity, diagnosed with first time unilateral stroke, 4 - 20 weeks post-stroke onset, resulting in hemiparesis with foot drop will be recruited. The number of participants was estimated based on previously reported studies. Hyun et al found significant differences in gait endurance measured by 6MWT when using AFO compared to using no AFO with 15 participants in a similar study (Hyun, Kim, Han, & Kim, 2014). In another study by Carse et al, gait velocity and gait symmetry were found to be significantly better with 8 participants (Carse, Bowers, Meadows, & Rowe, 2014). Therefore, for our study, the potential participant number was projected as 20.

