To assess the effects of practice on the gait measures, AFO's will be randomized for practice. Participants will be randomized for which AFO they will wear first (the PLS or the DA AFO), by drawing out of a hat. Again randomization without replacement technique will be used. Then the participant will be provided with the selected type of AFO to practice with for the following week using a prescribed wearing schedule. At the end of the one-week practice time, the primary investigator will obtain the same measurements obtained at baseline with the participant wearing the type of AFO that was used to practice the week before. The same testing conditions and order of testing that were used at baseline will be employed. Once measurements are completed, the participant will be provided with the second type of AFO and will be asked to wear for one week using the same prescribed wearing schedule as before. Final measurements will be taken after completion of the one-week practice using the second type of AFO with the same testing conditions and orders. At the conclusion of testing each participant will be asked which AFO they will prefer to use for their daily ambulatory needs for descriptive analysis. All data collected will be de-identified and stored in the Primary Investigator's secure personal computer. Any documents used such as Participant information sheet will be securely locked in a cabinet at Texas Woman's University where only the Primary investigator will have access.

Data Analysis

The following statistics will be calculated using SPSS for Windows. Descriptive statistics will be calculated for all demographic data including age, height, weight, time since onset Fugl Meyer lower extremity assessment score and AFO preference.

Differences in gait endurance will be analyzed using a 2x2 repeated measures ANOVA. Differences in gait symmetry, and gait velocity between the two AFO conditions and two practice conditions will be analyzed using two separate 2x2 repeated measures MANOVA. If assumption of sphericity is not met, Greenhouse-Geisser statistic will be used. An alpha level of .05 will be used to determine significance of differences, with a Bonferroni correction applied as needed to protect against Type I error.

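### Practice order is randomised over two consecutive weeks but left out of the 2x2 models, so the post-practice AFO comparison loses power and is biased if completers are unequal by order

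*Combined protocol and SAP*

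**What the plan says.** Under Experimental design: "The research design for this experimental study will be a 2 factor within subject repeated measures 2x 2 design". The factors are AFO type (Double Adjustable, DA, or Posterior Leaf Spring, PLS) and practice time (baseline, after one week).

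Under Data Analysis: "Differences in gait endurance will be analyzed using a 2x2 repeated measures ANOVA". Symmetry and velocity each get a 2x2 repeated measures MANOVA. No order, week or period term appears anywhere.

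Under Procedures, both AFOs are tested in one session at baseline. For practice, "Participants will be randomized for which AFO they will wear first (the PLS or the DA AFO), by drawing out of a hat", and "Again randomization without replacement technique will be used". After the week-1 test, "Once measurements are completed, the participant will be provided with the second type of AFO and will be asked to wear for one week". Then "Final measurements will be taken after completion of the one-week practice using the second type of AFO". Each AFO is therefore tested after practice only at the end of its own week, and no washout is described.

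On recovery, the Introduction says: "It is reported that the majority of the gait improvements occur within the first 6 months following the onset of stroke". The Participants section enrols people "diagnosed with first time unilateral stroke, 4 - 20 weeks post-stroke onset".

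**The concern.** The practice-time level labelled as after one week mixes measurements taken one and two weeks after baseline. Which AFO falls in which week depends on the randomised order. By the protocol's own account participants enter during the period of fastest gait recovery, so some change between the two weeks should be expected. Because order is known for every participant, that change can be separated from error. The planned models do not separate it.

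Hypothesis 2, the AFO difference after practice, is the most exposed. The study has 20 participants and no power calculation, so an inflated standard error makes it easier to miss a real difference. If the two orders lose different numbers of participants, part of the recovery trend is also read as an AFO effect. The plan has no drop-out allowance or missing-data rule.

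**Working it through.** **Inputs from the documents.** N = 20 (Participants); alpha 0.05, taken as two-sided because the hypotheses speak of a difference; two practice orders drawn without replacement. Equal slips are stated for the test-order draw, and 10:10 is assumed for the practice draw as well.

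**Inputs not in the documents (assumptions).** The weekly gain g, the SD and the drop-out rate. Here sd is the SD of the within-person post-practice difference *within an order*, and g is set at 0.25, 0.5 and 1.0 sd.

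**The plan's own figure.** N = 20 was set by analogy with studies of 15 and 8 participants, so there is no power figure to reproduce. For orientation, a paired t-test with 20 participants has 80% power for an effect of 0.66 sd. That effect is used below, without Bonferroni correction.

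**Model.** Let d = DA minus PLS after practice and tau = the AFO effect.

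- DA first: d = tau − g + error
- PLS first: d = tau + g + error

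**Planned analysis (mean of all d).**

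- Bias = g × (n PLS-first − n DA-first)/n. At 10:10 it is 0. At 10:8 it is g × 2/18 = 0.11g in size, and at 10:6 it is g × 4/16 = 0.25g. The sign depends on which order has more completers.
- Reported SE over true SE at 10:10 = sqrt(1 + (g/sd)² × 20/19). At g = 0.5 sd this is sqrt(1 + 0.25 × 20/19) = 1.12.

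**Analysis with order.** The mean of the two order-specific means, with the pooled within-order variance and n − 2 degrees of freedom. Under this model the bias is 0 and type I error is 5% at every split.

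**Results for the post-practice comparison, by simulation.**

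| | g = 0.25 sd | g = 0.5 sd | g = 1.0 sd | Order in model |
|---|---|---|---|---|
| 10:10, SE ratio | 1.03 | 1.12 | 1.43 | 1 |
| 10:10, type I error | 4.4% | 2.9% | 0.6% | 5% |
| 10:10, power | 78% | 72% | 49% | 80% |
| 10:10, N for 80% power (even N) | 22 | 24 | 34 | 20 |
| 10:8, size of bias (sd) | 0.03 | 0.06 | 0.11 | 0 |
| 10:8, power, imbalance against the effect | 69% | 59% | 28% | 74% |
| 10:8, power, imbalance with the effect | 77% | 74% | 60% | 74% |

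At 10:6 against the effect, with g = 0.5 sd, power is 43% unadjusted and 66% with order.

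**Other terms of the 2x2 model.** The baseline comparison carries no g. The AFO main effect carries g/2 and the interaction carries g. With each effect scaled to 80% power at g = 0, equal SDs at both times and a baseline/follow-up correlation of 0 to 0.5, power at 10:10 is 79%, 76–78% and 64–70% for the main effect, and 78–79%, 72–76% and 49–64% for the interaction. The practice main effect is untouched by order, because each completer supplies one week-1 and one week-2 value.

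**Two-outcome MANOVA (illustration).** With self-selected and fast pace correlated 0.5–0.8 and the same g for both, power is 77%, 68–70% and 37–43%, against about 80% with order.

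**The case against.** The strongest reply is that randomising the order already deals with the week effect. With 20 completers split equally, the AFO estimate has no period bias and the test is conservative, so only efficiency is lost. That is right for the balanced case.

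The size is also unknown. The large losses need a weekly gain as big as the whole SD of the AFO difference, and the protocol's statement about six months of recovery does not establish such a rate. At g = 0.25 sd or less the balanced loss is about 2 points of power. This stands, and the g = 1.0 column is only the end of a range.

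The bias is conditional on the split that occurs. If drop-out is unrelated to order, its expectation is zero, and losing 4 of 20 at random gives a 10:6 split with probability 2 × 210/4845 = 9%. This also stands, but the single realised estimate would still be shifted. Early stopping makes imbalance more likely: if 15 of 20 slips were drawn (an assumption), a 9:6 or 10:5 split has probability 4704/15504 = 30%.

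Three limits of scope also hold:

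- False positives stay at or below about 5% at 10:10, 10:8 and 10:6, but reach roughly 6–7% at 10:5 with g of 0.5 to 1.0 sd.
- A common additive g suits endurance and velocity better than the symmetry ratio, which recovery can move up or down towards 1.0. The MANOVA figures are therefore a velocity-type illustration.
- The main effect suffers less than the interaction only if baseline and follow-up differences are correlated. At correlation 0 both lose the same power.

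None of this is a reason to leave out a known, randomised design factor.

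**Conclusion.** The concern holds and should be fixed. The omission is certain from the text; the size of the harm is not. With equal orders the harm is lost power: 2 points at g = 0.25 sd, about 8 at 0.5 sd and about 30 at 1.0 sd. With unequal completers the post-practice comparison and the interaction also carry a bias that follows recovery rather than the AFO, and the main effect carries half of it.

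The statement that balance removes bias assumes no differential carryover from week 1 to week 2. If carryover differs between the AFOs, the planned and the order-adjusted estimates are both off by half that difference. The power figures further assume a true effect of 0.66 sd and an uncorrected two-sided alpha of 0.05; a Bonferroni correction would change the power of both analyses.

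**What to change.** Add randomised practice order (DA first or PLS first) as a between-subject factor in the ANOVA and in both MANOVAs, crossed with AFO type and practice time. A main effect of order alone would not absorb the ±g split. Report the post-practice AFO difference as the unweighted mean of the two order-specific differences, with its 95% confidence interval, and give the number of completers in each order.

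State as a limitation that there is no washout and that the order term does not remove carryover. A first-week-only comparison of DA and PLS, adjusted for the same AFO's baseline value, could be added as a sensitivity analysis. It would be between-subject with about 10 per order, and so imprecise.

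The cost is a change of analysis wording. Order is known from which AFO was tested at the second session, so no new data are needed. Error degrees of freedom fall from 19 to 18. If g were in fact zero, power would fall from 80.0% to 79.8% at 10:10, from 75% to 74% at 10:8, and from 70% to 66% at 10:6.

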Patients with stroke resulting in hemiparesis and foot drop are affected by gait impairments such as poor symmetry, decreased velocity, and decreased endurance. AFOs have been shown to be an effective intervention for improving gait parameters in individuals who are in the chronic stage of stroke recovery (Tyson, Sadeghi-Demneh, & Nester, 2013; Tyson & Kent, 2013). Although, the majority of gait improvements occur within six months of stroke (Kwakkel, Kollen, & Lindeman, 2004), the effect of early bracing with different types of AFOs on gait outcomes has not been investigated thoroughly.

Purpose of the study:

The purpose of this study will be to identify whether patients in the subacute stage of stroke, who demonstrate foot drop, will have better gait outcomes when using a Double Adjustable AFO, or a Posterior Leaf Spring AFO. A secondary purpose will be to determine whether one week of practice significantly changes gait outcomes with either of the AFO conditions.

Research Hypotheses

The research hypotheses of this study are as follows:

1. There will be a difference in gait endurance measurements, gait symmetry measurements and gait velocity measurements at baseline when using custom Double Adjustable AFO compared to a PLS AFO in patients in subacute stage of stroke.
2. There will be a difference in gait endurance measurements, gait symmetry measurements and gait velocity measurements after one week of practice when using custom Double Adjustable AFO compared to a PLS AFO in patients in subacute stage of stroke.
3. After a week of practice, there will be a difference in gait endurance measurements, gait symmetry measurements and gait velocity measurements compared to baseline measurements, when using either custom Double Adjustable AFO or a PLS AFO in patients in subacute stage of stroke.

Significance of Study

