a) Gait endurance will be measured using the Six Minute Walk Test (6MWT).

Participants will be asked to ambulate as far as possible in 6 minutes at a self-selected walking velocity through a well-lit indoor corridor. Participants will be informed when half of the time is over, otherwise no verbal cueing or encouragement will be provided. A gait belt will be used to ensure patient safety. If the participant needs to sit during the testing, that will be allowed.

However the timer will not be stopped for sitting rest breaks. The primary investigator will walk beside the patient, without influencing the speed of ambulation to ensure safety. The distance ambulated during the six minutes will be measured in feet using a measuring wheel and then converted to meters for data analysis.

b) Gait Symmetry will be measured using the temporospatial measurements from the GAITRite™ (CIR systems, Havertown, PA, USA) computerized gait analysis system. The GAITRite walking system used in this study is a 16 feet long x 3 feet wide portable walkway with embedded pressure sensors at 1.27 cm intervals along the length of the walkway. As the participant ambulates on the walkway, the pressure of the foot activates the sensors that record the person's steps. The data will be sampled at 1000 Hz. These measurements are then sent to a computer program that analyzes the specified temporal spatial parameters using the algorithm built into the special software. This data can be saved and exported to Microsoft Excel where the data can be further analyzed (*GAITRite electronic walkway technical reference, revision L. 2013.*) Step symmetry will be calculated using the ratio of the affected step length to the unaffected step length during self-selected velocity walk and fast paced velocity walk, with perfect symmetry defined as 1.0.

c) Gait velocity in cm/sec will also be assessed using the temporospatial measurements of the self-selected pace walk and fast paced walk from the GAITRite™ computerized gait analysis system.

Procedures:

All measurements will be obtained from each participant during three testing sessions and by only one researcher to avoid inter tester reliability issues. On the first measurement day, participants receive their custom DA AFO. The primary investigator will collect demographic

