data including age, height, weight, leg length measurements on each side, and Fugl-Meyer Lower Extremity Assessment of sensorimotor function. Then the gait outcomes will be measured using one of the two AFO conditions in random order. Two possible orders will be written on piece of paper and an equal number of possible order selections will be put in a hat. The participant will select the order of AFO condition by drawing out of a hat. Randomization without replacement will be used. Once the order of AFO wearing has been determined, data will be collected in the randomly selected order. Participants will be allowed to use any type of assistive device of their choice, but the same device will be used for all conditions.

First, the 6MWT will be administered with the participant wearing the first randomized AFO. Participants will be asked to ambulate as far as possible in 6 minutes at a self-selected walking velocity through a well-lit indoor corridor. A five minute seated resting will be provided before the next measurement is taken. Next, gait symmetry and gait velocity measurements will be obtained using the GAITRite system. Participants will be given a practice trial walk prior to beginning of the testing. Participants will be asked to walk at their comfortable self-selected walking velocity along the walkway. They will begin walking three meters from the start of the walkway and will stop walking two meters past the end of the walkway. The beginning and end of the walking area will be marked with red tape for visibility. The verbal instruction will be “Please walk from this red line to that red line at your comfortable speed safely”. A second personnel will be walking close to the participant outside of the walkway to ensure safety. After a five minute sitting break, participant will be asked to walk as fast as they can safely. The verbal instruction will be “Please walk from this red line to that red line as fast as you can safely”. The GAITRite system will be able to capture both gait symmetry and gait velocity measurements with the same walk. Three trials will be performed of the self-selected velocity walk and fast

paced velocity walk. The calculated mean of the three trials will be used for data analysis. After a 10 minute seated rest break, the second AFO condition will be used and measurements will be repeated in the same order described above.

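### If hypothesis 1 is tested inside the planned 2x2 models, anyone who misses session 2 or 3 also drops out of the baseline AFO comparison; one sentence would prevent this

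*Combined protocol and SAP*

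**What the plan says.** Procedures sets out the sessions: "All measurements will be obtained from each participant during three testing sessions". On day 1 both devices are tested, one after the other: "After a 10 minute seated rest break, the second AFO condition will be used and measurements will be repeated in the same order described above". Each participant then practises for a week with one AFO, and at session 2 "the primary investigator will obtain the same measurements obtained at baseline with the participant wearing the type of AFO that was used to practice". The other AFO is practised next and tested at session 3: "Final measurements will be taken after completion of the one-week practice using the second type of AFO with the same testing conditions and orders".

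Research Hypotheses, item 1, concerns day 1 only: "There will be a difference in gait endurance measurements, gait symmetry measurements and gait velocity measurements at baseline", comparing the Double Adjustable (DA) AFO with the posterior leaf spring (PLS) AFO. Hypothesis 2 is the same comparison after practice. Hypothesis 3 compares post-practice values with baseline.

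Data Analysis names these inferential methods and no others: "Differences in gait endurance will be analyzed using a 2x2 repeated measures ANOVA", and differences in symmetry and velocity "between the two AFO conditions and two practice conditions will be analyzed using two separate 2x2 repeated measures MANOVA". The software is SPSS ("The following statistics will be calculated using SPSS for Windows"), with no procedure named. The section does not say whether hypotheses 1 and 2 are tested within the 2x2 models or separately. It gives no missing-data rule and no analysis set. Participants projects 20 people from two earlier studies of 15 and 8, with no allowance for drop-out.

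**The concern.** A classical repeated measures ANOVA or MANOVA works on one complete row per participant. A person who finishes day 1 but misses session 2 or 3 has an incomplete row and is removed whole, including the two baseline values that hypothesis 1 needs. If the baseline comparison is taken from the 2x2 model, it would rest on fewer people than were measured for it, in a sample of only 20. If it is run as a separate paired test on day-1 data, the loss does not arise, but the plan names no such test. What is at stake is precision for one of three hypotheses, and a choice of analysis set that would otherwise be made after the data are in.

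**Working it through.** **The plan's own figure.** N = 20 comes without an effect size, SD, power or loss rate, so there is no calculation to reproduce. The loss numbers, effect sizes and two-sided testing below are assumptions. Alpha 0.05 is from Data Analysis.

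**Step 1: which session supplies which cell.** This holds for each outcome variable.

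| Cell | Session |
|---|---|
| DA, baseline | 1 |
| PLS, baseline | 1 |
| AFO practised first, after practice | 2 |
| AFO practised second, after practice | 3 |

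Hypothesis 1 uses the first two rows only. The 2x2 model uses all four. For symmetry and velocity, each cell holds two values (self-selected and fast pace), so each MANOVA needs 2 x 4 = 8 values per participant. The pattern of loss by session is the same.

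**Step 2: number available for hypothesis 1.** With k participants incomplete after day 1, the paired contrast on day-1 data has n = 20. Inside the 2x2 model it has n = 20 - k, that is 18 for k = 2 and 16 for k = 4.

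**Step 3: confidence interval.** The 95% half-width in SDs of the paired difference is t(0.975, n-1)/sqrt(n).

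- n = 20: 2.093/4.472 = 0.468
- n = 18: 2.110/4.243 = 0.497; ratio 0.497/0.468 = 1.06
- n = 16: 2.131/4.000 = 0.533; ratio 0.533/0.468 = 1.14

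**Step 4: power.** Two-sided paired t-test, noncentral t with n-1 degrees of freedom and noncentrality d x sqrt(n), alpha 0.05. The effect d = 0.66 SD is chosen because it gives 80% power at n = 20. The values 0.5 and 0.8 show the range.

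| d | n = 20 | n = 18 | n = 16 |
|---|---|---|---|
| 0.50 | 57% | 52% | 47% |
| 0.66 | 80% | 75% | 69% |
| 0.80 | 92% | 89% | 85% |

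**Step 5: would a mixed model on all observed cells help hypotheses 2 and 3?** Simulations with n = 20 and an unstructured covariance estimated from the data compared the complete-case SD of each estimate with the all-cell SD. A ratio above 1 favours the mixed model.

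- Hypothesis 2: about 0.98 to 1.03, so essentially no gain.
- Hypothesis 3, both later sessions missed: about 0.98 to 1.01, no gain.
- Hypothesis 3, session 3 alone missed: a gain of about 2% to 8%.

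With 4 of 20 incomplete, the simulated type I error of that mixed model for hypotheses 2 and 3 was about 6% instead of 5%.

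**The case against.** The strongest reply is that the harm needs two things the documents do not establish: that hypothesis 1 is tested inside the 2x2 model, and that people are lost. Follow-up is two one-week practice periods, and the $80 compensation is paid at completion (Funding), which may keep losses low. Both points stand, and they are why this is minor. They do not remove the point, because the plan leaves the test of hypothesis 1 open and one sentence settles it. The power figures also rest on a chosen effect size; the interval widening does not.

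Three stronger readings are tempting, and the documents support none of them.

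- A reader might infer that the plan will discard day-1 data. It does not say so; this follows only if hypothesis 1 is tested within the 2x2 model.
- A reader might infer that the baseline result will be biased. In a simulation with a true difference of 0.30 and loss confined to participants whose day-1 DA-minus-PLS difference was below average, the complete-case mean was 0.395, against 0.302 with all day-1 pairs. That pattern of loss is pure assumption. With random loss the complete-case mean was 0.302.
- A reader might infer that the ANOVA and MANOVAs should give way to a mixed model. Step 5 does not bear this out: the gain is confined to one hypothesis under one loss pattern, and it comes with a slightly raised type I error and an assumption that missingness is explained by the observed data.

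**Conclusion.** The point holds in conditional form. Both measurements for hypothesis 1 exist after day 1, yet the only named tests need cells from all three sessions. If hypothesis 1 is tested within those models and 2 or 4 of 20 are incomplete, its confidence interval is 6% or 14% wider than it need be, and at d = 0.66 SD power is 5 or 11 percentage points lower (80% to 75% or 69%). With no losses, or with a separate paired test, the cost is nil. The loss rate is not in the documents, so the actual size is unknown. This is a cheap improvement of minor severity, not an error in the plan.

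**What to change.** Add to Data Analysis: hypothesis 1 will be tested for each outcome (for symmetry and velocity, at each pace) as a paired DA-versus-PLS contrast on all participants with both day-1 measurements, whether or not they complete sessions 2 and 3; the number of participants in each AFO-by-time cell will be reported. These tests fall under the same Bonferroni provision that the section already contains.

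Keep the planned ANOVA and MANOVAs for hypotheses 2 and 3. A linear mixed model on all observed cells may be added as a sensitivity analysis only, labelled as such so that it is clear which test decides.

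The cost is a sentence or two of analysis text. No new data, visits or software are needed, and the paired contrast carries none of the mixed model's drawbacks.

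### The randomised day-1 AFO test order is left out of the analysis, so any first-versus-second test effect is counted as error in the baseline comparison (hypothesis 1)

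*Combined protocol and SAP*

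**What the plan says.** Hypothesis 1 (Research Hypotheses) is confined to baseline: "There will be a difference in gait endurance measurements, gait symmetry measurements and gait velocity measurements at baseline when using custom Double Adjustable AFO". The comparator is the PLS AFO.

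Procedures describes how those baseline data arise. "Then the gait outcomes will be measured using one of the two AFO conditions in random order". The hat holds equal numbers of the two orders and slips are drawn without replacement; the total number of slips is not given. In the first AFO the participant does the 6MWT and then the self-selected and fast GAITRite walks. "After a 10 minute seated rest break, the second AFO condition will be used and measurements will be repeated in the same order described above".

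A second, separate hat draw decides which AFO is worn in the first home week. After each week only the AFO just practised is tested.

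Experimental design fixes the factors: "The research design for this experimental study will be a 2 factor within subject repeated measures 2x 2 design", the two being AFO type and practice time. Data Analysis follows this. On endurance it says: "Differences in gait endurance will be analyzed using a 2x2 repeated measures ANOVA". The other two outcomes have the same two factors, but with MANOVA as the method: "Differences in gait symmetry, and gait velocity between the two AFO conditions and two practice conditions will be analyzed using two separate 2x2 repeated measures". No term for order, sequence or period appears, nor any check for an order effect, and no separate test of hypothesis 1 is named.

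**The concern.** Day 1 is a two-position crossover within one session. The second battery follows a complete first one, so fatigue could lower it, or familiarity could raise it. Participants may need contact-guard assistance (Participants) and may sit during the 6MWT (Instrumentation/Measurements), so a net position effect is plausible, although its sign and size are unknown.

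Randomising in equal numbers is meant to cancel this effect between the AFOs. The cancellation works on the estimate. It does not work on the standard error unless the analysis also uses the order: a shift known to go one way in one order group and the other way in the other remains in the residual. At stake is the power of hypothesis 1 in a trial whose sample size has no power calculation ("The number of participants was estimated based on previously reported studies"). If the orders end up unequal, part of the position effect also enters the estimate.

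Modelling practice order would not repair this. It comes from a different draw and governs different visits.

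**Working it through.** **Inputs from the protocol.** n = 20 (Participants: "Therefore, for our study, the potential participant number was projected as 20"); alpha .05 (Data Analysis), taken as two-sided because the hypotheses are non-directional; two day-1 orders in equal numbers (Procedures). The figure of 20 cannot be reproduced, because no effect size, SD, power or dropout rate is given.

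**Assumptions.** A hat of 10 + 10 slips. Position effect delta (second minus first test) of 0 to 1.0, in SDs of the DA-minus-PLS difference within an order group. A true AFO effect tau = 0.66 of the same SD, which gives a paired t-test 80% power at n = 20.

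**Model.** For participant i, D_i = tau + s_i·delta + e_i, with s_i = +1 if DA is tested second, -1 if PLS is second, and SD(e) = 1.

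**Order omitted.** The baseline contrast is a paired t-test on D with 19 df.
- Bias = delta·(n1 - n2)/n, where n1 and n2 are the numbers tested with DA second and PLS second. This is 0 at 10:10.
- Expected error variance at 10:10 = 1 + delta²·n/(n - 1). For delta = 0.5: 1 + 0.25 × 20/19 = 1.26, so the standard error is inflated by √1.26 = 1.12.

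**Order included.** The estimate is the mean of the two order-group means, with pooled within-order variance on 18 df. The shift s_i·delta leaves the residual.

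**Results at 10:10 (simulation).**

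| delta | error variance, order omitted | SE ratio | size, omitted | power, omitted | power, included |
|---|---|---|---|---|---|
| 0 | 1.00 | 1.00 | 5.0% | 80% | 80% |
| 0.25 | 1.07 | 1.03 | 4.4% | 78% | 80% |
| 0.5 | 1.26 | 1.12 | 2.9% | 72% | 80% |
| 0.75 | 1.59 | 1.26 | 1.5% | 63% | 80% |
| 1.0 | 2.05 | 1.43 | 0.6% | 50% | 80% |

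With order included, size stays at about 5% throughout. At delta = 0 the exact powers are 80.0% omitted and 79.8% included, so the lost degree of freedom costs about 0.2 points.

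**AFO main effect averaged over time.** Its per-person value is the mean of the baseline and post-practice differences, and only the first carries the shift, so the shift is delta/2. With an effect of 0.66 SD of that averaged difference, and an assumed correlation of 0 to 0.7 between the two differences, power with order omitted is about 79-80% at delta 0.25, 76-78% at 0.5 and 65-71% at 1.0.

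**Unequal orders.** With 10 + 10 slips and all 20 tested, the split is exactly 10:10. If fewer are analysed, with losses unrelated to order, the chance of an unequal split (hypergeometric) is 47% at 18, 58% at 16, 63% at 14, and certain at any odd number. At 8:6 the bias is 2/14 = 1/7 of delta, or 0.07 SD when delta is 0.5. A split such as 12:8 with 20 participants needs more than 20 slips in the hat. There, with delta 0.5, the bias is 4/20 × 0.5 = 0.10 SD, and power with order omitted is about 85% or 57% depending on the sign of delta, against 78% with order included.

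**The case against.** The strongest reply is that the design already controls order: equal slips, drawing without replacement, seated rests of 5 minutes within the battery and 10 minutes between AFOs, a practice walk before the GAITRite trials, and the same assistive device throughout. That stands as far as it goes. With a 10:10 split the estimate is unbiased and a significant baseline result remains valid. What the design does not do is take the position effect out of the error term.

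Second, delta is wholly assumed. Fatigue and warm-up pull in opposite directions and may nearly cancel; at 0.25 SD the loss is only about 2 points. This also stands. Nothing in the protocol favours the upper half of the range.

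Third, Data Analysis names the 2x2 models, not a baseline test, and the main effect is hit less. That is correct. But hypothesis 1 is a baseline statement, so a baseline contrast is needed to answer it.

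Fourth, simply adding order as a between-subject factor would be a poor repair. In repeated-measures output the between-subject order term compares the groups' overall means and is not the position effect. The factor would also enter the post-practice comparison, where one AFO is tested per visit and day-1 position has no meaning. If practice order were added as well, a full factorial would leave 16 error df and four cells averaging five. These points are sound and determine the form of the fix.

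A reader might infer that the baseline comparison is biased as planned, or that false positives are inflated. The protocol does not support either. Balance is the intended outcome of the draw, the bias has expectation zero over the randomisation, and at balance the size falls below .05.

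**Conclusion.** The point holds as a loss of efficiency. The plan randomises day-1 test order and then leaves it out, so any position effect inflates the error of the hypothesis 1 contrast. At 10:10, power falls from 80% to about 78%, 72% and 50% for position effects of 0.25, 0.5 and 1.0 SD, and the test becomes conservative. The main effect loses less. Bias needs unequal realised orders and is then delta·(n1 - n2)/n.

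These figures rest on an assumed delta, an assumed AFO effect of 0.66 SD and, for the imbalance chances, an assumed hat of 10 + 10 slips. They show what could be lost, not what will be. The change is worth making because the order is already drawn for each participant and using it costs almost nothing. It is not a ground for calling the baseline result invalid.

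**What to change.** In Data Analysis, state that hypothesis 1 will be tested, for each outcome, on the day-1 DA-minus-PLS difference, with day-1 test order coded +1/-1 as the single covariate. For the 6MWT this is one regression. For symmetry and for velocity it is the multivariate version, with the self-selected and fast-pace differences as the two responses.

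The intercept, which weights the two orders equally, is the AFO effect. The order coefficient is the position effect and should be reported as such. It corresponds to the order-by-AFO term at baseline, not to the between-subject order main effect. Day-1 order need not enter the post-practice comparison.

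Cost: a short addition to the plan, no new data, and one error degree of freedom (19 to 18), about 0.2 points of power if there is no position effect.
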